***Axitinib dose titration:**

Individual patient dose titration of axitinib (escalation from starting dose) is permitted on protocol therapy, at the discretion of the treating physician, if the following criteria are met for an individual patient:

1. Two consecutive cycles are completed at a given dose without any adverse reactions $>$ Grade 2 (according to the Common Toxicity Criteria for Adverse Events [CTCAE]).
2. The patient is normotensive, and not receiving anti-hypertension medication.

For patients \geq 18 years old, when a dose increase from 5 mg twice daily is recommended, the axitinib dose may be increased by 1 mg/dose twice daily (for example, from 5 mg twice daily to 6 mg twice daily, etc), up to a maximum of 10 mg twice daily. No more than 1 dose titration can occur in each 2-cycle period per the criteria above. Refer to the table in [Section 5.2.1.1](#) for additional detail.

For patients < 18 years old, see [Appendix IV](#) for dose titration nomograms. No more than 1 dose titration can occur in each 2-cycle period per the criteria above. The maximum titration dose is as per the Dose Level 3 table in [Appendix IV](#).

See [Section 5.0 for Dose Modifications based on Toxicities](#).

Following completion of a cycle, begin next cycle on Day 29 or when criteria to begin cycle are met, whichever occurs later.

4.5 Arm C: Nivolumab

4.5.1 Therapy Delivery Map – Arm C: Nivolumab

Each cycle lasts 28 days (4 weeks). Absent disease progression or unacceptable toxicity, patients may continue on protocol therapy for up to 2 years duration or completion of 26 cycles, whichever comes first.

This TDM is on 3 pages. A copy of this TDM will be used for each cycle; please enter the cycle # below.

Patient COG ID number

DOB

Criteria to start each cycle: ANC \geq 1000/ μ L, platelet count \geq 75,000/ μ L without transfusion support.

See [Section 5.0](#) for other requirements related to any ongoing toxicities.

DRUG	ROUTE	DOSAGE	DAYS	IMPORTANT NOTES
Nivolumab (IND# [REDACTED]) Do not use commercial supply	IV over 30 minutes, or per institutional guidelines	If \geq 18 years old:	240 mg/dose OR 480 mg/dose	1, 15
		If < 18 years old:	3 mg/kg/dose	1 only
				For patients < 18 years old: Maximum dose is 240 mg/dose administered on Days 1 and 15.

Enter Cycle #: _____

Ht _____ cm Wt _____ kg

BSA _____ m²

Date Due	Date Given	Day	Nivolumab mg	Cycle 1 Studies	Cycles 2 – 26 Studies
			Enter calculated dose above and actual dose administered below		
		1	mg	a – q	a – q
		...			
		8		a*, c*, d – f	
		...			
		15	mg [#]	a, c – f	(c – f)*
		...			
		22		a*, c*, d – f	
		...			
		28			r
		29	Begin next cycle on Day 29 or when criteria to begin cycle are met, whichever occurs later. See Section 4.5.3 . See Section 7.0 for end of treatment evaluations.	* For patients < 18 years of age only.	

[#] Day 15 nivolumab does not apply to patients \geq 18 years of age, receiving 480 mg/dose on Day 1 only.

See [Section 5.0](#) for Dose Modifications for Toxicities.

4.5.2 Required Observations in Arm C: Nivolumab

All baseline studies must be performed prior to starting protocol therapy unless otherwise indicated below.

- a. Physical Exam: Prior to each cycle, and additionally during Cycle 1:
 - For patients < 18 years old, perform weekly
 - For patients \geq 18 years old, perform every other week
- b. Height/Weight: Prior to each cycle.
- c. CBC/diff/platelets: Prior to each dose of nivolumab, and additionally during Cycle 1:
 - For patients < 18 years old, perform weekly
 - For patients \geq 18 years old, perform every other week
- d. Creatinine, bilirubin: Prior to each dose of nivolumab, weekly during Cycle 1 only.
- e. Electrolytes, BUN, Ca^{2+} , PO_4^{3-} , Mg^{2+} : Prior to each dose of nivolumab, weekly during Cycle 1 only.
- f. AST/ALT/Albumin: Prior to each dose of nivolumab, weekly during Cycle 1 only.
- g. PT/INR: Prior to every odd-numbered cycle (e.g., Cycles 1, 3, 5, etc.).
- h. TSH: Prior to every odd-numbered cycle (e.g., Cycles 1, 3, 5, etc.).
- i. Urinalysis/Urine Protein/Creatinine: Prior to Cycles 1, 2, 3 and then prior to every odd-numbered cycle (e.g., Cycles 5, 7, 9, etc.).
- j. Lipase: Prior to each cycle.
- k. Pregnancy Test: Female patients of childbearing potential require a negative pregnancy test within 72 hours prior to starting treatment and then prior to every odd-numbered cycle (e.g., Cycles 3, 5, 7, etc.); sexually active patients must use an acceptable method of birth control.
- l. ECG: Prior to every 4th cycle starting Cycle 1 (e.g., Cycles 1, 5, 9, etc.).
- m. MUGA or ECHO: Prior to every 4th cycle starting Cycle 1 (e.g., Cycles 1, 5, 9, etc.).
- n. GFR or Creatinine Clearance: As clinically indicated. See [Appendix VII](#) for GFR calculation.
- o. Immune biomarkers (patient consent is required): Before treatment initiation and before Day 1 of Cycles 2, 3, and 9 (within 72 hours prior to Day 1 dosing), and within 3 weeks after the last dose of study treatment. See [Section 15.2.1](#) for complete details.
- p. Tumor Tissue (patient consent is required): Before treatment initiation and at any time tumor tissue is obtained (i.e. surgery). See [Section 15.2.2](#) for complete details.
- q. Specimens for Banking (patient consent is required): See [Section 15.2.3](#) for complete details.
- r. Tumor Imaging: After Cycles 2, 4, 6, 9, 12, and then every 4 cycles; at relapse. See [Section 16.2](#) for complete details.

This listing only includes evaluations necessary to answer the primary and secondary aims. OBTAIN OTHER STUDIES AS REQUIRED FOR GOOD CLINICAL CARE.

Comments

(Include any held doses, or dose modifications)

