2.5.2 Nivolumab

2.5.2.1 Adult patients (≥ 18 years of age)

A fixed nivolumab FDA Approved dose of 240 mg IV every 2 weeks or 480 mg IV every 4 weeks will be used for adult patients.

With Amendment #5, adults will have the option to receive nivolumab on one of the above mentioned schedules as both are FDA approved and felt equivalent with regards to efficacy in adult patients.

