[#] Day 15 nivolumab does not apply to patients \geq 18 years of age, receiving 480 mg/dose on Day 1 only.

[%] Required pharmacokinetics only applies to pediatric patients (age $<$ 18 years old).

^{*}Cycles 2 and 3 only. Patients should be instructed to hold the AM axitinib dose until after the pre-dose PK has been drawn. See [Section 5.0](#) for Dose Modifications for Toxicities.

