4.5.3 Treatment Details – Arm C: Nivolumab

Each cycle lasts 28 days (4 weeks). Absent disease progression or unacceptable toxicity, patients may continue on protocol therapy for up to 2 years duration or completion of 26 cycles, whichever comes first.

Criteria to start each cycle: ANC \geq 1000/ μ L, platelet count \geq 75,000/ μ L without transfusion support. See [Section 5.0](#) for other requirements related to any ongoing toxicities.

Nivolumab: IV over 30 minutes or per institutional guidelines

Age	Dose and Days
\geq 18 years old	Either 240 mg/dose on Days 1 and 15 OR 480 mg/dose on Day 1 only
< 18 years old	3 mg/kg/dose (maximum 240 mg/dose) on Days 1 and 15

The risk of infusion reactions with nivolumab is low and no pre-medications are required. Monitoring for infusion reactions should be per institutional guidelines. Please refer to [Section 5.3.2](#) for suggested infusion reaction management guidelines.

Nivolumab will be distributed by the Division of Cancer Treatment and Diagnosis (DCTD), NCI. Do not use commercial supply.

See [Section 5.0](#) for Dose Modifications based on Toxicities.

Following completion of a cycle, begin next cycle on Day 29 or when criteria to begin cycle are met, whichever occurs later.

Patients on Arm C that meet protocol defined criteria of disease progression prior to Cycle 22 of therapy, may cross-over and receive Arm A (combination) therapy. Total therapy received on study AREN1721, either on Arm A, Arm C, or for patients that cross-over, is not to exceed 26 cycles total or 2 years, whichever comes first.

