5.2.8 Dose Modifications for Cardiac Toxicity:

Patients who experience \geq Grade 3 left ventricular systolic dysfunction must be removed from protocol therapy and referral to a cardiologist is recommended.

5.2.9 Dose Modifications for Diarrhea:

If Grade 3 (> 3 day duration) or Grade 4 therapy-associated diarrhea is experienced by a patient despite maximal use of anti-diarrheal medications the dose of axitinib should be reduced by one dose level for subsequent cycles (see [Section 5.2.1](#)).

5.3 **Dose Modifications for Nivolumab**

Adverse events (both non-serious and serious) associated with nivolumab exposure may represent an immunologic etiology. These adverse events may occur shortly after the first dose or several months after the last dose of treatment. Nivolumab must be withheld for drug-related toxicities and severe or life-threatening AEs as per Table 2 below. Please also refer to [Appendix V](#) for suggested management guidelines. Please note some of the guidelines include references to medications which may not be appropriate for patients < 18 years of age.

Table 2. Dose Modification Guidelines for Nivolumab-Related Adverse Events

Toxicity	Hold Treatment for Grade	Timing for Restarting Treatment	Treatment Discontinuation
Diarrhea/Colitis (age \geq 18 years)	2-3	Toxicity resolves to Grade 0-1	Toxicity does not resolve within 6 weeks of last dose or inability to reduce corticosteroid to 0.15 mg/kg (up to 10 mg) or less of prednisone or equivalent per day within 6 weeks
	4	Permanently discontinue	Permanently discontinue
Diarrhea (age < 18 years)	2-3 if not reversible within 7 days and related to drug	Toxicity resolves to Grade 0-1 (evaluate for colitis)	Toxicity does not resolve within 6 weeks of last dose or inability to reduce corticosteroid to 0.15 mg/kg (up to 10 mg) or less of prednisone or equivalent per day within 6 weeks
	4	Permanently discontinue	Permanently discontinue
AST, ALT, or Increased Bilirubin (age \geq 18 years)	2	Toxicity resolves to Grade 0-1	Toxicity does not resolve within 6 weeks of last dose
	3-4	Permanently discontinue (see exception below) ^a	Permanently discontinue
AST, ALT (age < 18 years)	2-3 if not reversible within 7 days and related to drug	Toxicity resolves to Grade 0-1 (monitor AST/ALT at least twice per week until resolution)	Toxicity does not resolve within 6 weeks of last dose
	4	Permanently discontinue (see exception below) ^a	Permanently discontinue

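### For adults dosed on Days 1 and 15, the Arm C delivery map drops the Day 15 labs from Cycle 2 on, although Section 4.5.2 requires them before every nivolumab dose

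*Combined protocol and SAP*

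**What the plan says.** Section 4.5.3 gives adults in Arm C two schedules: "Either 240 mg/dose on Days 1 and 15 OR 480 mg/dose on Day 1 only". Section 2.5.2.1 dates the choice: "With Amendment #5, adults will have the option to receive nivolumab on one of the above mentioned schedules".

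Section 4.5.2 lists the required observations. Items c to f are CBC, creatinine and bilirubin, electrolytes, and AST/ALT/albumin. All four are due before each dose of nivolumab. Item f reads "AST/ALT/Albumin: Prior to each dose of nivolumab, weekly during Cycle 1 only". The only age split is in item c, and it concerns the extra Cycle 1 tests. The list closes with "This listing only includes evaluations necessary to answer the primary and secondary aims".

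The Arm C delivery map in Section 4.5.1 has two marks in its Day 15 row:

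- The dose carries #, a footnote that removes the Day 15 dose only for adults on 480 mg.
- The studies for Cycles 2 to 26 are entered as `(c – f)*`, and the map's one asterisk note reads "For patients < 18 years of age only".

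The map is a working form: "This TDM is on 3 pages. A copy of this TDM will be used for each cycle".

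Section 5.3 makes dosing depend on toxicity: "Nivolumab must be withheld for drug-related toxicities and severe or life-threatening AEs as per Table 2 below".

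**The concern.** The map and the list give different instructions for the same visit, and the protocol does not say which prevails. The map is the form completed every cycle, so a site could reasonably take its age limit as the rule and give an adult the Day 15 dose without pre-dose labs.

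Those labs drive decisions in Table 2. For adults, Grade 2 AST, ALT or bilirubin means holding nivolumab, and Grade 3 or 4 means stopping it, subject to the table's exception. Renal grades also trigger holds. The adult liver rule is the tighter one: under 18, Grade 2 or 3 AST/ALT leads to a hold only if it is drug-related and not reversible within 7 days. The map thus leaves out the mid-cycle check in the age group with the stricter rule. A dose given without the listed labs would also be a protocol deviation.

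**Working it through.** The plan states no figure on this point, so the check is a side-by-side reading followed by a count.

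**Day 15 in Arm C** (map from 4.5.1, list from 4.5.2)

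| Patient | Nivolumab on Day 15? | Map, Cycle 1 | Map, Cycles 2–26 | List, items c–f, Cycles 2–26 |
|---|---|---|---|---|
| Under 18 | Yes | a, c–f | c–f | Required |
| Adult, 240 mg Days 1 and 15 | Yes | a, c–f | None | Required |
| Adult, 480 mg Day 1 | No | a, c–f | None | Not required |

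Only the middle row conflicts, and only from Cycle 2. The Cycle 1 entry has no asterisk and agrees with the list for all ages.

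**Does the Cycle 1 phrase in items d to f end the pre-dose rule?** No. It limits the weekly testing. Item c describes its Cycle 1 tests as additional to the pre-dose ones. The map itself schedules Day 15 labs for children in Cycles 2 to 26, which would make no sense if the pre-dose rule stopped after Cycle 1.

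**Arm A.** The Arm A map (4.3.1) has the same pattern, `(c – g)*`, and Section 4.3.2 has the same pre-dose rule. That map also carries a second asterisk note, on PK: "Cycles 2 and 3 only. Patients should be instructed to hold the AM axitinib dose". The symbol is therefore less clean there, and Arm A is supporting evidence only. Item g is blood pressure, which is not part of this point because Section 5.2.5.3 has adults monitor it at home twice weekly.

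**Count.** For an adult on Days 1 and 15 who completes n cycles:

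- total doses = 2n
- doses in the disputed cell (Day 15 of Cycles 2 to n) = n − 1

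| n | Disputed / total | Share | Source of n |
|---|---|---|---|
| 5 | 4 / 10 | 40.0% | Assumed: 5 months × 30.44 / 28 = 5.4 cycles |
| 9 | 8 / 18 | 44.4% | Assumed: 8.2 months × 30.44 / 28 = 8.9 cycles |
| 26 | 25 / 52 | 48.1% | Protocol limit; 26 × 28 = 728 days, within 2 years |

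The 5 and 8.2 months are PFS figures for anti-VEGF therapy in Section 2.1.1. They are not nivolumab data and serve only to illustrate shorter treatment.

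**The case against.** **The mark may be misread.** The point turns on one superscript, and the dosing table at the head of the Arm C map is out of alignment in the text copy. A misread mark is unlikely, however. The # and the * appear as distinct marks in the same Day 15 row, the asterisk is used consistently on Days 8 and 22, and the Arm A map shows the same asterisk on its own Day 15 entry.

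**The list governs and is in front of the user.** The map's letters have no meaning without the list, and if both belong to one form, staff see the pre-dose rule every cycle. That lowers the risk but does not remove it. The form would then contradict itself, and nothing in the protocol ranks one part over the other.

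**The consequence is small.** Day 1 labs still occur every cycle, so Table 2 would be applied every 4 weeks, the interval accepted for adults on 480 mg. This stands as a limit on the harm. The two cases still differ: the adult on 480 mg has labs before every dose, while the adult on 240 mg would be re-dosed mid-cycle without them.

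**The size is uncertain.** This also stands. The share of adults on two-weekly dosing could be anything from none to all, and only the 26-cycle count comes from the protocol alone.

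**The age limit may be intended.** The list would then be the text in error, and a correction would still be needed. The documents give no reason for such a limit. The two-schedule option for adults came with Amendment 5, which suggests that the asterisk was not updated.

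**Conclusion.** The concern holds. It is an internal inconsistency in an operative instruction: from Cycle 2, an adult in Arm C on 240 mg every two weeks needs Day 15 labs under Section 4.5.2 and has none scheduled under the map in 4.5.1. It touches n − 1 of 2n doses in such a patient, at most 25 of 52. The conclusion rests on the asterisk having the one meaning given in the Arm C map.

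The harm is conditional on a site following the map over the list, and no actual missed test is shown. Children and adults on 480 mg are not affected. No bias between arms is shown, and the PFS analysis, alpha and sample size are untouched. A correction is warranted because a pre-dose safety check is at stake and the repair is simple.

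**What to change.** In the Arm C map, replace the asterisk on the Day 15 studies for Cycles 2 to 26 with the existing # mark. Extend the # footnote so that adults on 480 mg are exempt from the Day 15 dose and, from Cycle 2 on, from the Day 15 studies. Leave the Cycle 1 Day 15 entry unmarked, because Section 4.5.2 asks for those tests in all patients. The Day 15 labs then apply to everyone who is dosed that day.

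Make the same change in the Arm A map, and give its PK note a symbol of its own.

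If the sponsor did intend the age limit, the observation lists should be amended instead, with the reason given.

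The cost is a footnote edit on two maps. Measured against the lists, it adds no test (Arm A blood pressure, item g, is already listed before each dose). For a site that has been following the map, it restores up to 25 sets of labs per adult over 26 cycles.

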4.5.3 Treatment Details – Arm C: Nivolumab

Each cycle lasts 28 days (4 weeks). Absent disease progression or unacceptable toxicity, patients may continue on protocol therapy for up to 2 years duration or completion of 26 cycles, whichever comes first.

Criteria to start each cycle: ANC \geq 1000/ μ L, platelet count \geq 75,000/ μ L without transfusion support. See [Section 5.0](#) for other requirements related to any ongoing toxicities.

Nivolumab: IV over 30 minutes or per institutional guidelines

Age	Dose and Days
\geq 18 years old	Either 240 mg/dose on Days 1 and 15 OR 480 mg/dose on Day 1 only
< 18 years old	3 mg/kg/dose (maximum 240 mg/dose) on Days 1 and 15

The risk of infusion reactions with nivolumab is low and no pre-medications are required. Monitoring for infusion reactions should be per institutional guidelines. Please refer to [Section 5.3.2](#) for suggested infusion reaction management guidelines.

Nivolumab will be distributed by the Division of Cancer Treatment and Diagnosis (DCTD), NCI. Do not use commercial supply.

See [Section 5.0](#) for Dose Modifications based on Toxicities.

Following completion of a cycle, begin next cycle on Day 29 or when criteria to begin cycle are met, whichever occurs later.

Patients on Arm C that meet protocol defined criteria of disease progression prior to Cycle 22 of therapy, may cross-over and receive Arm A (combination) therapy. Total therapy received on study AREN1721, either on Arm A, Arm C, or for patients that cross-over, is not to exceed 26 cycles total or 2 years, whichever comes first.

5.0 DOSE MODIFICATIONS FOR TOXICITIES

5.1 Definitions of Dose-Limiting Toxicities (DLT)

DLT will be defined as any of the following events that are possibly, probably, or definitely attributable to protocol therapy.

NOTE: Dose-limiting hematological and non-hematological toxicities are defined differently. The Study Chair should be notified of any suspected or confirmed DLT.

5.1.1 Hematological DLT

5.1.1.1 Hematological dose-limiting toxicity is defined as:

- Grade 4 thrombocytopenia (platelet count $< 25,000/\mu\text{L}$) or Grade 4 neutropenia for > 7 days (see [Section 5.2](#)), not due to malignant infiltration.

5.1.1.2 Other hematological dose-limiting toxicities:

- Any Grade 2 arterial thromboembolic events (including cerebrovascular ischemia, peripheral or visceral arterial ischemia).
- Any \geq Grade 3 venous thromboembolic event.
- Any thrombotic event requiring systemic anti-coagulation.
- Any \geq Grade 2 hemorrhage.

5.1.2 Non-hematological DLT

5.1.2.1 Any Grade 3 or Grade 4 non-hematological toxicity attributable to the investigational drug with the specific exclusion of:

- Grade 3 proteinuria (urine protein/ creatinine (P/C) ratio > 1.9 for age < 18 ; urine protein $\geq 3.5 \text{ g}/24 \text{ hours}$ for age 18 and greater) unless it is confirmed with a second measurement within 72 hours.
- Grade 3 liver enzyme elevation, including AST/ALT that returns to levels that meet eligibility criteria within 7 days of study drug interruption and that does not recur upon study drug rechallenge.
- Grade 3 GGT, if checked. (Note: monitoring GGT is not required for this study)
- Grade 3 serum electrolyte elevation that returns to baseline within 7 days and does not require systemic immunosuppression.
- Grade 3 asymptomatic lipase elevation that resolves to meet the eligibility criterion within 7 days of study drug interruption and that does not recur upon study drug re-challenge.
- Grade 3 or 4 amylase or lipase abnormalities that are not associated with diabetes mellitus (DM), associated liver or gall bladder inflammation clinical manifestations of pancreatitis and which decrease to \leq Grade 2 within 7 days.
- Grade 3 diarrhea ≤ 3 days duration.
- Grade 3 nausea and vomiting of less < 3 days duration.
- Grade 3 or 4 fever < 5 days duration.
- Grade 3 infection < 5 days duration.
- Grade 3 rash/oral lesion that resolves to Grade ≤ 1 within 7 days.
- Fever greater than 40°C of ≤ 24 hr duration.
- Grade 3 fatigue that resolves to Grade ≤ 2 within 7 days.

- Grade 3 creatinine increased that resolves to Grade ≤ 1 or baseline within 7 days.
- Grade 3 pleural effusion that resolves per [Section 5.2.6](#).
- Grade 3 hypophosphatemia, hypokalemia, hypocalcemia or hypomagnesemia responsive to oral supplementation.

5.1.2.2 Grade 2 uveitis, eye pain, or blurred vision that does not respond to topical therapy and does not improve to Grade 1 prior to the next scheduled dose.

5.1.2.3 Grade 2 non-hematological toxicity requiring systemic immunosuppressive therapy, including but not limited to, autoimmunity of the lung, heart, kidney, bowel, CNS, pituitary or eye, with the specific exclusion of:
a. Grade 2 pleural effusion that resolves per [Section 5.2.6](#).
b. Drugs will be held for Grade 2 cardiac dysfunction pending evaluation.

5.1.2.4 Grade 2 endocrine toxicity requiring hormone replacement, with the exception of Grade 2 hypothyroidism, thyroiditis, and thyroid dysfunction adequately managed with thyroid hormone replacement (see [Section 5.3](#)).

5.1.2.5 Grade 2 adrenal insufficiency.

5.1.2.6 Grade 2 colitis or Grade 2 diarrhea attributable to protocol therapy that persists for > 7 days.

5.1.2.7 Any non-hematological toxicity requiring > 7 days delay in therapy.
NOTE: Allergic reactions that necessitate discontinuation of study drug will not be considered a DLT.

5.1.2.8 Dose-limiting hypertension

- Any Grade 4 hypertension.
- Any Grade 3 hypertension that persists for > 14 days despite adequate antihypertensive treatment.

5.1.2.9 Any Grade 2 non-hematological toxicity that persists for ≥ 7 days and is considered sufficiently medically significant or sufficiently intolerable by patients that it requires treatment interruption.

5.2 Dose Modifications for Axitinib

5.2.1 Axitinib Dosing Nomogram

5.2.1.1 For patients \geq 18 years of age

Dose Level	Axitinib Dose (mg PO BID)
-3 [#]	2
-2	3
-1	4
1*	5
2	6
3	7
4	8
5	9
6	10

* Starting dose

[#] If a patient was most recently dosed at the lowest dose level and requires a subsequent dose reduction, the patient must be removed from protocol therapy.

